### **Inclusion Criteria for Patients**

Participants must be of age 18-70 years, and have had TBI in the last 12 months prior to inclusion and presence of persistent TBI symptoms at the time of inclusion as confirmed by the co-investigator physicians.

### **Exclusion Criteria for all Participants**

- 1) Use of neuro- or psycho-active medications as published in recommendations [26]
- 2) Active use of illicit drugs
- 3) History of epilepsy
- 4) History of any other brain lesions including tumors, infectious, vascular, or metabolic lesions
- 5) Severe or recent heart diseases
- 6) Alcoholism
- 7) Pregnancy
- 8) The presence of metallic objects in the body; dental implants are fine but people with pacemakers are to be excluded; anything that is unsafe under MRI would be considered unsafe for TMS [26].
- 9) Lack of ability to adequately communicate (understand, read, speak) in English and understand the experimental protocol.
- 10) Pending litigation (i.e., patients with pending actions regarding disability reports, litigation, or other kinds of financial compensation).

Participants will receive the details of the study, and be asked to sign a written consent form prior to experiments. Upon meeting the eligibility criteria and providing informed consent, each patient participant will be randomly assigned to either treatment or sham groups; this assignment will not be revealed to the patients until the end of study. *The Sham Group's participants will be offered a course of treatment after the study is finished if the results show improvement beyond the placebo for the participants in Treatment Group.* Patients will be thoroughly assessed by the medical collaborators for their symptoms, and localization of the damage to the brain. The cognitively healthy Control Group will not receive any rTMS treatment. All participants will complete a series of cognitive and mental assessments, and EVestG assessments. The Control Group will go through a lesser number of questionnaires as there is no need for run concussion severity assessment on control group. The details of the study procedure are described below, and Table 1 summarizes the study protocol.

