## Introduction

### a. Rationale

Traumatic brain Injury (TBI) occurs when a sudden trauma causes either transient or permanent brain damage. In some literature, the term “concussion” is used to refer to the most common (mild) type of TBI. It is defined as an immediate and transient impairment of neural functions, such as the alteration of consciousness, balance and/or visual disturbances, due to a direct blow to the head or after a blow elsewhere that is transmitted to the head. In other literature, mostly neurological journals (and in this proposal), mild TBI (mTBI) and concussion are used interchangeably.

Every three minutes, there is a TBI case in Canada [3], and 50,000 Canadians sustain brain injuries each year [4]. Motor vehicle crashes and traffic-related incidents are major causes of TBI; 40% of TBI cases in Manitoba are due to car accidents [5]. Transport Canada reports that the road accident rate of the province of Manitoba is greater than the national average [6]. According to MPI’s 2011/12 annual report, there was an 89% increase in brain injury claims from 146 in 2010/11 to 276 in 2011/12 [5].

The majority of patients with mTBI recover in the first 2-4 weeks; the recovery time is much longer (a few years) for those with severe TBI. In general, the fastest improvement occurs in the first six months after injury and the patient may continue to get better over a period of up to two years. However, many survivors of severe TBI and mTBI continue to experience disabling persistent post-TBI symptoms including somatic and emotional symptoms (sleep disturbances, fatigue, headache and emotional changeability) [7], as well as cognitive [8,9], visual [10-15], and vestibular abnormalities [16,17]. Any of these adverse consequences of TBI impact the individual's quality of life and functionality for years after the injury. In fact, half of the hospitalized TBI patients develop TBI-related long-term or permanent disability [18], and over 70% of people diagnosed with severe TBI require long-lasting care and support [19]. In addition, TBI is strongly associated with subsequent disabling neurological disorders including Alzheimer's and Parkinson's diseases [20].

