### Theme 1: Applying rTMS treatment and its evaluation by neuropsychological and clinical assessments

1. Recruit people (from Riverview Health Center and also from [name] referrals), who have had a head injury within the past two to 12 months, have a clear diagnosis of TBI, and have persistent post-TBI symptoms. Collect standard neuropsychological assessment data at baseline.

2. Enroll the study participants into a “Sham Group” and a “Treatment Group” with a three-week protocol, and apply the treatment.
3. Record spatio-temporal assessments before and after treatment sessions, and examine the efficacy of rTMS treatment on the post-TBI symptoms by standard clinical and neuropsychological assessments by statistical analysis.

Theme 2: Monitoring treatment efficacy by objective measures, EVestG and spatio-temporal assessments

4. Record EVestG data with all its seven current stimuli at baseline (before the treatment) and immediately after treatment and also four and eight weeks after the last treatment.
5. Analyze EVestG data for extracting the optimum measures (biofeatures) showing the changes due to rTMS treatment.
6. Optimize (reduce the number of stimuli if possible) the EVestG recording protocol upon the results of Objective 5.
7. Examine the statistical correlation of the EVestG biofeatures representing the TBI recovery with data from the clinical and neuropsychological assessments as well as spatio-temporal assessments (derived in Objective 3).

Theme 3: Evaluating the objective measures of EVestG and spatio-temporal assessments in Control group

8. Recruit 20 age-and-gender-matched individuals with no history of head injury and record their EVestG data four times with a similar schedule to that of TBI patients, and investigate the consistency of the EVestG data between the sessions and compare with those of people with TBI during treatment.
9. Run the spatio-temporal assessments at the same sessions of EVestG recording in the Control Group and examine the effect of learning on the performance in these assessments.

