### **Study Protocol**

#### **Study Population/Participants**

A total of 20 individuals with a clear diagnosis of TBI within the last 12 months (as confirmed by their treating Neurologist, Psychiatrist or Medical Rehab Physiatrist, who are the co-investigators in this study) prior to the commencement of this study will be recruited from Riverview Health Center patient and [name] clinic patient population. Ten patients will be randomly assigned to **Treatment Group** and 10 others to **Sham Group**. Neither the patients, nor the clinical assessors will know the sham versus real treatment group assignment. In addition, as one of the objectives of this study is to evaluate the EVestG assessment as a

diagnostic and monitoring tool, 20 age-and-gender-matched cognitively healthy volunteers will be recruited as controls for the EVestG assessment. The healthy **Control Group**'s participants must not have any history of TBI and also meet other exclusion criteria for patients group listed below.

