### **Data analysis**

**EVestG Biofeature Extraction** – The NEER algorithm [52] will be used to locate and extract vestibular neural events. The interval histograms of the neural events are also used to extract the basic statistical properties of the neural firings such as probability density function (pdf), mean and variance, as well as fractal dimension, kurtosis and skewness of the signal. The features extracted from all tilts will be investigated to determine biofeatures specific to a concussion. The extracted biofeatures, e.g. fractal dimension, kurtosis and skewness of the potentials' distribution, from the recorded signal will be compared between Sham and Treatment Groups.

[figure not shown]
**Statistical Analysis, Clustering, Decision Making and Validation** – After data collection, the multivariate Analysis of Variance (MANOVA) statistical test will be run to determine the significant differences of any of the extracted biofeature measures between the sessions and the Control Group and the Treatment and Sham Groups. In all instances, a p-value less than 0.05 is considered significant. Cross correlation analysis will also be used to find the correlation between these measures and the neuropsychological assessments scores. Once the statistically significant features among the groups are found, the classic approach of discriminant analysis with leave-one-out routine (for robust results in small size data) will be run to investigate whether concussion cases can be identified. An important issue to address is the membership assignment of the subjects. Since there may not be confirmed and solid clinical and neuropsychological assessments for the recovery from the TBI post-symptoms, we will also run unsupervised (blind) clustering of the objective measures followed by our recently developed diagnostic decision making algorithm to identify TBI recovery. The diagnostic and monitoring algorithms will be checked with the updated diagnoses of the clinical symptoms (by the referring physician) and the neuropsychological evaluations.

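### Treatment v Sham comparisons take no account of time since injury, although the protocol says recovery is generally fastest in the first six months and enrols patients up to 12 months after injury

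*Combined protocol and SAP*

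**What the plan says.** - **Prognosis.** Introduction, a. Rationale, says of TBI in general that "the fastest improvement occurs in the first six months after injury" and that improvement may go on for up to two years.
- **Entry window.** The inclusion criteria ask that patients "have had TBI in the last 12 months prior to inclusion and presence of persistent TBI symptoms at the time of inclusion". Objective 1 under Theme 1 gives a narrower window, for people who "have had a head injury within the past two to 12 months". Study Population/Participants plans "A total of 20 individuals with a clear diagnosis of TBI within the last 12 months", counted back from the start of the study and not from the patient's own inclusion.
- **Allocation.** "Ten patients will be randomly assigned to" the Treatment Group and ten to Sham. Under the exclusion criteria, "each patient participant will be randomly assigned to either treatment or sham groups". No stratum, block or minimisation factor is given. Matching on age and gender concerns only the healthy controls.
- **Follow-up.** Table 1 runs from baseline to week 12.
- **Analysis.** Data analysis plans a MANOVA of the EVestG biofeatures "between the sessions and the Control Group and the Treatment and Sham Groups", with no covariate named. For symptoms, Objective 3 promises a statistical analysis of the clinical and neuropsychological assessments without naming a model.

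**The concern.** Patients can enter on both sides of the boundary that the protocol itself draws. Twelve weeks is about 2.8 months. A patient who enters two months after injury is therefore followed to about 4.8 months, wholly inside the period of fastest recovery. A patient who enters at ten months is wholly outside it. Measuring the baseline score and repeating it captures where each patient starts, not how fast each would have improved untreated.

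With ten per arm, chance can put noticeably more early patients in one arm. The comparison then mixes natural recovery with response to rTMS and can mimic or hide an effect. Even when the arms balance, the difference in recovery stays in the error term. The study is a pilot, but it tests at p < 0.05, and whether sham patients are offered active treatment depends on the result.

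**Working it through.** The documents give no effect size, SD or power, so there is no stated figure to reproduce.

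**Inputs from the documents:** 20 patients, 10 per arm; boundary at six months; significance level 0.05 (taken as two-sided, since the sidedness is not stated).

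**Assumptions:** the number of early patients (under six months) is K = 6 to 14 of 20. Early patients improve D = 0.5, 1.0 or 1.5 SD more than late ones. The SD of change within the early and late groups is 1. The true effect is 1.0 SD.

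**1. Chance of imbalance.** With arms fixed at ten, the number of early patients in one arm is hypergeometric. For K = 10:

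P(7:3 or worse) = 2 × (120² + 45² + 10² + 1²) / 184,756 = 2 × 16,526 / 184,756 = 17.9%.

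The chance that the arms differ by four or more early patients is 17.0% for K = 8 or 12 and 14.1% for K = 6 or 14.

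On a continuous scale, with months since injury uniform over 0-12, the SD of the difference in arm means is √(2/10) × 12/√12 = 1.55 months. The means then differ by more than two months in about 20% of trials (12% if uniform over 2-12).

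**2. Shift in the contrast.** At 7:3 the unadjusted difference moves by D × (0.7 − 0.3) = 0.4D, that is 0.2, 0.4 or 0.6 SD.

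**3. False positives.** Averaged over all allocations, the unadjusted test keeps its level (simulated 4.9-5.0%). Given a 7:3 split towards the active arm and no true effect, false positives in favour of rTMS are 5.6%, 9.6% and 12.6%, against a nominal 2.5%. Adjustment returns them to about 2.5%.

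**4. Precision.** With half the patients early, the unadjusted variance is 1 + D²/4 = 1.06, 1.25 or 1.56. A true effect of 1.0 therefore becomes a standardised effect of 0.97, 0.89 or 0.80.

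Simulated power (8,000 or more trials per setting; runs agree to about one point):

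| Analysis | D = 0.5 | D = 1.0 | D = 1.5 |
|---|---|---|---|
| Unadjusted | 53-54% | 47% | 39% |
| Adjusted, six-month indicator | 54% | 54% | 53% |
| Adjusted, linear months | 53% | 52% | 48% |
| Stratified at six months and adjusted for the indicator | 56% | 56% | 56% |

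These rows assume a step at six months. If the gradient is linear in time, linear months does better than the indicator. If there is no gradient (D = 0), adjustment costs about 2-3 points.

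**The case against.** - **The gradient may be weak here.** The six-month statement is about TBI in general. The same paragraph says most mild cases recover in two to four weeks, and the requirement for persistent symptoms removes those patients. A reader might infer that the protocol calls time since injury a strong predictor in the enrolled group. It does not, and D is assumed throughout. At D = 0.5 the average gain in power is nil. This stands, and it limits the size of the point.
- **Randomisation already protects validity.** It does, on average. A reader might infer a biased trial or an inflated overall error rate; step 3 of the working shows neither. What remains is the error in the trial that happens to be unbalanced, and the lost precision.
- **The allocation may be restricted.** A reader might infer unrestricted randomisation. The text fixes ten per arm and is otherwise silent on method, so only the absence of any stated use of time since injury can be criticised.
- **No clinical model exists to adjust.** The MANOVA covers EVestG biofeatures, and a reader might wrongly take it for the efficacy analysis of symptoms. The clinical model is a larger gap. That makes the covariate something to write into the model when it is specified; it does not remove the need.
- **Severity matters too.** The Rationale also ties recovery time to severity. True, but 20 patients cannot carry many covariates, and the six-month boundary is the protocol's own.

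**Conclusion.** The concern holds in a limited form. The protocol states a general recovery gradient, enrols across it, and uses time since injury in neither allocation nor analysis. An imbalance of four or more early patients between arms has probability 14-18% for K between 6 and 14, and shifts the unadjusted contrast by 0.4D. For a true effect of 1.0 SD, adjusting for the six-month indicator gains nothing worth counting at D = 0.5, about 7 points of power at D = 1.0 and about 14 at D = 1.5. It also removes the conditional error at each value. All of this rests on the assumed D, on a step at six months, and on a within-group SD of 1.

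A reader might also infer that stratified randomisation is required. The figures do not support that: it adds about 2-3 points over adjustment alone and is a matter of judgement in 20 patients.

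**What to change.** 1. Record the date of injury and prespecify time since injury at baseline as a covariate, beside the baseline score, in every Treatment v Sham comparison of change, clinical and EVestG. Healthy controls have no injury date, so fit these comparisons in the 20 patients, apart from any comparison with controls.
2. Fix one form in advance. Under six months v six months or more matches the protocol's own statement. Linear months is defensible if a steady gradient is expected. Do not choose after seeing the data.
3. Report time since injury by arm.
4. Reconcile the entry windows and their reference dates in Objective 1, Study Population/Participants and the inclusion criteria, so that the covariate has one definition.
5. Optional, if enrolment has not begun: randomise in blocks within the two six-month strata. This needs two allocation lists, and arms may end slightly unequal if the last blocks are incomplete.

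**Cost:** eligibility already requires the injury to be dated, so little new data is needed. The covariate takes a sentence once the clinical model is written, and one residual degree of freedom, or about 2-3 points of power if there is no gradient.

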### **rTMS Treatment Procedure**

The treatments will be administered daily (five days/week) for two weeks, followed by three days on the third week (total of 13 treatments). Patients of both real and sham treatment groups will undergo rTMS treatment of 1.5-second duration trains of pulses at 20 Hz for a total of 25 trains with intertrain interval of 10 seconds applied to DLPFC bilaterally. Thus, there will

be a total of 1500 pulses per two sides of the brain per day, which is well within the safety limit of the rTMS application.

During the intertrain intervals, the patients will be presented a series of objects and actions and asking to name them. The images will be projected on the wall in front of patient with duration of three seconds for each image. The aim is to keep the brain active while we stimulate it with rTMS. Prior to each treatment session, the patient's resting motor threshold (RMT) will be measured using a single pulse of TMS, noting the intensity necessary to cause a small twitch in the thumb finger in three consecutive pulses. Then, the 70 mm cooled figure-8-coil will be placed on the head at a location for optimal stimulation of the DLPFC at the intensity of 100% of the RMT. Each rTMS treatment session will take approximately 20 minutes.

The same protocol will also be used while using sham stimulation. For the sham stimulation we will attach a 2-cm-thick piece of wood with the same size and shape as the coil, under the coil; the wood is an insulator and dissipates all the energy of the pulses, while the sensations and the sounds do transmit through the wooden piece. This is currently used for our rTMS treatment of Alzheimer's patients.

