### **b. Background**

This project proposes to use two novel technologies for treatment and the monitoring of therapy efficacy: rTMS and EVestG.

**Transcranial Magnetic Stimulation (TMS)** – TMS is a relatively new, but popular and well-tolerated, neuromodulation method that is emerging as a therapeutic tool for a variety of neurological conditions [1]. TMS is a noninvasive procedure based on the principles of electromagnetic induction, whereby a magnetic field pulse (generated by the coil placed on the scalp) produces electrical currents in underlying neural tissue of the brain. The repetitive application of TMS (rTMS) pulses can modulate cortical excitability, either increasing or decreasing it, even well beyond the duration of stimulation. This has shown to have therapeutic potentials for several neurodegenerative diseases, i.e. Parkinson, stroke and psychiatric disorders such as depression [25-26].

rTMS has been increasingly used and found to be a promising noninvasive treatment for an array of brain disorders such as depression (FDA approval in 2008), migraine (FDA approval for prophylaxis in 2008), post-traumatic stress disorder, obsessive-compulsive disorder, stroke, Parkinson's disease, Alzheimer's disease, and epilepsy, as well as tinnitus and a variety of pain syndromes [27-29]. There are several reports of case studies that show beneficial effects of rTMS treatment on patients with severe TBI [30-33]. Four clinical trials are currently in progress to examine the efficacy and safety of rTMS in the treatment of TBI [34]. It is proposed that potential targets of rTMS therapeutic application in TBI patients could be TBI-related symptoms and functional sequences [35]. A number of studies demonstrate that rTMS treatment improves cognitive functions (i.e. attention/concentration, memory, executive functions/working memory, learning, psychomotor speed, language, emotional processing, and global cognitive functioning) [36,37], gait [38], balance [39], symptoms of depression [40] and anxiety [41], tinnitus and auditory processing [42], visual acuity [43], sleep quality [44], motor function of upper and lower limb(s) [45,46], spasticity [47], and reduces fatigue [48]. The same pattern is likely to be translated to patients with above-named symptoms due to TBI.

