The fundamental rationale for therapeutic use of rTMS is based on compelling evidence that rTMS is able to modulate long-term neural plasticity at the network level [39,49,50]. These lasting neuroplastic changes induced by rTMS would likely help promote the recovery of brain function and decrease the burden of disabling sequelae of TBI, based on the evidence that it helps slowing cognitive decline in Alzheimer's patients.

We are currently applying high-frequency (20 Hz) rTMS bilaterally over the dorsolateral prefrontal cortex (DLPFC) as treatment for Alzheimer's [51]. We envision using a similar protocol and same location of the brain for TBI treatment with rTMS, as four case studies [30-33] that applied rTMS to TBI patients, also applied it to DLPFC brain regions at the either 10 or 20 Hz frequency. The DLPFC plays an important role in cognitive (executive, attention, memory) function of the brain due to its interconnectedness with other brain regions. The DLPFC

coordinates function with the rest of the brain and also helps to shift between tasks, and therefore has a role in working memory [50].

In general, rTMS is considered to be a safe, non-invasive, painless and harmless procedure. Review papers on rTMS tolerability and safety when applied to populations with depression (and on pregnant women with depression), Parkinson's disease, Huntington's disease, epilepsy, and anxiety have reported mild discomforts including mild tension headache (due to stimulation of the peripheral muscles in the scalp) after the session that diminishes within a couple of hours and some mild annoyance during the stimulation. The induction of migraine by rTMS is rare, and indeed rTMS to the left DLPFC has been used to reduce migraine headache. rTMS at high frequencies increases the risk of seizure induction. Although the risk of seizure at frequencies lower than 30 Hz is very low, in our study, we exclude people with a history of seizure as well as those with large ischemic scars (as that also increases the risk of seizure induction).

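### The sham is described as absorbing all pulse energy, which does not fit the protocol's own account of TMS; the field is more likely reduced than abolished, and no planned check would reveal a failed blind.

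*Combined protocol and SAP*

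**What the plan says.** All places are in the combined protocol and SAP.

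- **rTMS Treatment Procedure, the sham.** "we will attach a 2-cm-thick piece of wood with the same size and shape as the coil, under the coil". The stated reason it works is that "the wood is an insulator and dissipates all the energy of the pulses, while the sensations and the sounds do transmit" through it. The coil is still discharged: "The same protocol will also be used while using sham stimulation". The only support given is that the same sham is in use in the group's Alzheimer's study.
- **rTMS Treatment Procedure, threshold.** Before each session the "resting motor threshold (RMT) will be measured using a single pulse of TMS", and treatment intensity is set at 100% of it. The text does not say whether the spacer is on or off in the sham arm during this step.
- **Background, mechanism.** "a magnetic field pulse (generated by the coil placed on the scalp) produces electrical currents in underlying neural tissue of the brain".
- **Background, tolerability.** The listed discomforts include "mild tension headache (due to stimulation of the peripheral muscles in the scalp", as the protocol puts it.
- **Study Population/Participants.** "Neither the patients, nor the clinical assessors will know the sham versus real treatment group assignment". The person delivering the stimulation is not mentioned.
- **Assessments and analysis.** The neuropsychological measures, the spatio-temporal assessments, the Data analysis section and Table 1 contain no treatment guess, sensation rating, sham-credibility item or field measurement.

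**The concern.** The Treatment versus Sham contrast is the trial's efficacy answer. It also decides whether sham patients are later offered active treatment, since that offer depends on a gain over placebo. Both uses assume that the sham delivers nothing to the brain and cannot be told apart from active treatment.

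The protocol supports the first assumption with an argument that does not follow from its own account of how TMS works, and it gives no data for either. If some effective field remains, the contrast shrinks. If patients can recognise the sham, the symptom and mood scores (RPQ, MADRS) can drift toward apparent benefit. The two biases run in opposite directions, so neither a positive nor a null result could be read with confidence unless something were recorded that bears on them.

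**Working it through.** **1. The plan's own figure.** The one reproducible number in the stimulation section is the daily pulse count: 1.5 s × 20 Hz × 25 trains = 750 per side, and 750 × 2 = 1500. It agrees with the text and is not in dispute. The documents give no power calculation and no field strength.

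**2. The statements side by side.**
- Induction (Background) against insulation (Treatment Procedure): a magnetic pulse is not stopped by a material because that material does not conduct electricity. On the protocol's own mechanism, the wood's evident effect is to move the coil 2 cm away.
- Scalp-muscle stimulation (Background) against transmitted sensation (Treatment Procedure): if no pulse energy reaches the scalp, the muscle component cannot be reproduced. If it is reproduced, not all the energy was dissipated. This conflict covers pulse-induced muscle sensation only.

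**3. How much field 20 mm removes.** Assumptions, none of them from the documents: an ideal figure-8 coil of two adjacent opposed loops of radius R, free space, and a point at distance d below the junction. The stated 70 mm coil is read as R of about 35 mm, with 30-45 mm as the range.

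A(d) ∝ 2 ∫ R cos θ dθ / √[2R²(1 + cos θ) + d²], θ from 0 to 2π

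The induced field is proportional to A, so the fraction left is |A(d + 20)| / |A(d)|.

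| R (mm) | d = 10 mm | d = 15 mm | d = 20 mm |
|---|---|---|---|
| 30 | 0.32 | 0.35 | 0.38 |
| 35 | 0.35 | 0.39 | 0.41 |
| 40 | 0.38 | 0.42 | 0.44 |
| 45 | 0.41 | 0.45 | 0.47 |

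The range is 32-47%. A conducting-sphere check (85 mm radius, coil 3 mm off the scalp, both assumed) gives 0.34, 0.37 and 0.39 for R = 35 mm at the same depths. No value is near zero. The ratios describe the sham dose only if the threshold was measured without the spacer.

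**4. What each fault could do at 10 v 10.** Two-sample t-test, 18 df, two-sided 0.05 assumed (the plan gives 0.05 without sidedness), noncentrality δ√(10/2). Effect and bias sizes are illustrations.
- Weakly active sham: an assumed true effect of 1.325 SD has power 0.80. If sham keeps 10%, 25% or 50% of the effect, power is 0.71, 0.56 or 0.29.
- Recognisable sham: with no true effect, an assumed bias of 0.2, 0.3 or 0.5 SD raises the chance of a significant result favouring active from 0.025 to 0.06, 0.09 or 0.18.

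**5. What a guess question could detect.** With 20 patients and a cut-off of 15 or more correct, the exact one-sided error is P(X ≥ 15 | 20, 0.5) = 0.021. Power is 0.42, 0.80 or 0.99 if 70%, 80% or 90% guess correctly.

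**The case against.** The case on the other side has real substance.

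- **Sensation can pass through wood.** The protocol attributes one effect, headache, to scalp-muscle stimulation. It does not say that all sensation is induced current. Tapping, vibration and sound could well be transmitted. This stands: a reader might infer that the protocol's account rules out any transmitted sensation, and it does not. Reading pulse energy as electromagnetic energy only eases the sensation conflict, but leaves the claim that wood absorbs it unsupported.
- **Residual field is not residual activity.** At 100% of threshold, 39% of the field is about 39% of motor threshold, and energy scales with the square (0.39² ≈ 0.15). The documents give no level below which rTMS is inert, so the bias toward no effect may be nil. This stands.
- **Perceived sensation and expectancy bias cannot be sized.** One might infer that scalp sensation falls in proportion to the field, or attach an SD value to unblinding in this trial. Nothing in the documents anchors either.
- **Threshold pulses.** It is tempting to say that every sham patient feels real pulses before each session. The text does not say so, and isolated pulses aimed at a thumb twitch are an imperfect reference for 20 Hz trains.
- **Context.** This is a 10 v 10 pilot with patient and assessor blinding stated and assignment withheld from patients until the end. That limits the severity, but a pilot is a natural place to measure whether a sham is credible.

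**Conclusion.** The concern holds in a limited form. The statement that the spacer dissipates all pulse energy is unsupported and inconsistent with the protocol's induction account. For pulse-induced scalp-muscle sensation it also conflicts with the tolerability text. Under the idealised coil assumptions, roughly a third to a half of the induced field remains (32-47%), so the field is reduced and not abolished.

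That the sham is active, or that patients can recognise it, is possible but not shown. What is established is that the plan asserts a property it does not document and records nothing that would reveal a failed blind. The net direction of any bias cannot be determined from the documents. The point deserves correction before the contrast is described as benefit over placebo; it does not invalidate the design.

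**What to change.** 1. **Correct the sham sentence.** State that the spacer increases coil-to-scalp distance and reduces, but is not shown to abolish, the induced field. Cite any field measurement the group holds. Describe the comparison as active versus reduced-field sham.
2. **Reconcile the Background and rTMS Treatment Procedure sections**, and state whether the spacer is on or off in the sham arm when the motor threshold is measured. If off, sham patients have a real-pulse reference. If on, the threshold is set through the spacer. The documents should say which applies.
3. **Add a simple blinding check.** Early in the course, at an existing session, ask each patient for a treatment guess (treatment / sham / don't know) and a scalp-sensation rating. Repeat the guess for patients and assessors at the week 4 visit. Report answers by arm, descriptively.

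The guesses should not become a rule that bars reporting of RPQ or MADRS differences. By week 4 they are partly confounded with perceived benefit, and a chance-level result in 20 patients would not show that blinding held.

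Cost: protocol wording and a few questions at contacts already scheduled. Downsides: the check finds only marked unblinding and cannot repair it, it says nothing about residual field, and the sham claim becomes less favourable. No change to stimulation is proposed.
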